### **7.8. Genetics**

Information regarding genetic research is included in [Appendix 10](#)

### **7.9. Value Evidence and Outcomes**

#### **7.9.1. Psoriasis Symptom Diary**

The Psoriasis Symptom Diary was developed to assess daily self-reports of psoriasis symptoms and the functional impact related to the underlying pathophysiology of the disease [Strober, 2013]. Questions about how severe and how bothersome various signs and symptoms are to the subject are answered using an 11-point numerical rating scale ([Appendix 5](#)). In this study, subjects will be asked to complete the Psoriasis Symptom Diary questionnaire at the clinic during the scheduled visits.

## 8. DATA MANAGEMENT

- For this study subject data will be entered into GSK/bioskin defined eCRFs, transmitted electronically to GSK or designee and combined with data provided from other sources in a validated data system.
- Management of clinical data will be performed in accordance with applicable GSK standards and data cleaning procedures to ensure the integrity of the data, e.g., removing errors and inconsistencies in the data.
- Adverse events and concomitant medications terms will be coded using MedDRA (Medical Dictionary for Regulatory Activities) and an internal validated medication dictionary, GSKDrug.
- eCRFs (including queries and audit trails) will be retained by GSK, and copies will be sent to the investigator to maintain as the investigator copy. Subject initials will not be collected or transmitted to GSK according to GSK policy.

## 9. STATISTICAL CONSIDERATIONS AND DATA ANALYSES

Refer to the reporting and analysis plan (RAP)/statistical analysis plan (SAP) for additional details regarding data analyses. Reporting will be performed in accordance with applicable GSK and/or contract research organization (CRO) standards.

### 9.1. Hypotheses

No formal hypothesis tests are planned. Descriptive statistics will be used to assess the key objectives of this study: evaluation of safety, tolerability, systemic exposure and clinical effect of topically applied GSK2981278 ointment in subjects with plaque psoriasis.

### 9.2. Sample Size Considerations

#### 9.2.1. Sample Size Assumptions

Sample size is based on feasibility and the estimated number of subjects expected to provide reasonable information on the key objectives of the study.

For Part A:

Summary statistics, such as mean % of reduction in TPSS, mean % reduction in PGA and mean % of reduction in PASI will be estimated. With 8 evaluable subjects, precisions on these estimates are assessed as below.

Endpoint	Assumptions	Sample Size	95%CI estimate
Mean % reduction in TPSS	50% reduction with 20% standard deviation will be observed	N=8	33.3% - 66.7%
Mean % reduction in PGA	50% reduction with 30% standard deviation will be observed	N=8	24.9%-75.1%
Mean % reduction in PASI	50% reduction with 25% standard deviation will be observed	N=8	29.1% -70.9%

### For Part B:

With 15 subjects (10 in GSK2981278 arm and 5 in the Vehicle arm), the power to detect difference between GSK2981278 arm and the vehicle arm in terms of TPSS reduction, and PASI reduction are assessed below:

Endpoint	Assumptions	Sample Size (API:Vehicle)	Power to reject* $H_0: API=Vehicle$ (Alpha=5%)
Mean % reduction in TPSS	50% reduction in GSK arm and 20% reduction in Vehicle with 20% standard deviation will be observed	N=10:5	71.7%
Mean % reduction in PASI	50% reduction in GSK arm and 10% in Vehicle with 20% standard deviation will be observed	N=10:5	92.1%

\*2-sample t test

API- Active Pharmaceutical Ingredient

### 9.2.2. Sample Size Re-estimation or Adjustment

No sample size re-estimation or adjustment is planned.

## 9.3. Data Analysis Considerations

### 9.3.1. Analysis Populations

Per Protocol (PP) analysis set will include all randomized subjects who comply closely with the protocol (e.g. have sufficient exposure). PP analysis set details will be defined in the RAP/SAP. The PP analysis set will be the primary set for efficacy analyses.

Safety analysis set will include all subjects exposed to at least 1 application of study product. The safety analysis set will be the primary set for safety analyses.

Pharmacokinetic (PK) analysis set will include subjects with at least one sample collected and analyzed for plasma drug concentration. The PK analysis set will be the primary set for PK analyses.

### **9.3.2. Interim Analysis**

No interim analysis is planned.

## **9.4. Key Elements of Analysis Plan**

### **9.4.1. Primary Analyses**

#### **Safety and tolerability analyses:**

Extent of exposure will be summarized. A by-subject listing of data on subject exposure to study drug will be produced. AEs will be tabulated according to the current version of MedDRA. Frequencies and percentages will be presented overall, for each system organ class, and for each preferred term. Summaries of treatment-emergent AEs, treatment-related AEs, AEs leading to discontinuation of study product applications, and SAEs will be completed. AE onset, severity, relationship to study product, action taken, and outcome will be listed by subject.

Each quantitative laboratory test will be summarized at every scheduled time point. The number of subjects with abnormal values based on values relative to the laboratory normal ranges will be summarized for each assessed time point. A listing of laboratory data for subjects with values out of the laboratory normal range will be provided.

Vital sign value and change from baseline at Week 8 for each vital sign parameter will be summarized using descriptive statistics. A listing of vital signs and a listing of change from baseline for vital signs will be provided.

ECG value and change from baseline at every scheduled time point for each ECG parameter will be summarized using descriptive statistics. The ECG will be evaluated by the investigator as “Normal”, “Abnormal, not clinically significant”, and “Abnormal, clinically significant”. A summary of ECG findings will be provided. Also, a listing of ECG values and a listing of ECG findings will be generated.

If applicable, liver event data will be listed.

#### **Systemic exposure/Pharmacokinetic Analyses (Part A):**

Plasma concentrations of GSK2981278 will be determined. For **Part A**, if the concentration data permits, the following PK parameters will be calculated: AUC(0-t), AUC(0- $\tau$ ), Cmax, tmax, and half-life (t1/2), steady state assessments such as C $\tau$  and R0.

#### **Clinical effect analyses (Part B):**

Mean percentage change in TPSS, PGA and PASI scores from baseline to each study visit will be summarized based on the per protocol analysis set.

The data may also be summarized using the following measures as needed:

- proportion of subjects who achieve a PGA score of 0 or 1 and a minimum 2-grade improvement from baseline to each study visit
- proportion of subjects with  $\geq 50\%$  improvement in PASI from baseline to each study visit
- change in PASI from baseline to each study visit

In addition, statistical comparisons may be made as necessary between GSK arm and the Vehicle arm for mean percentage change from baseline to Week 8 in terms of TPSS, PGA and PASI score.

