Objectives	Endpoints
Primary	

 
To evaluate the safety and tolerability of topically applied GSK2981278 and its vehicle in subjects with plaque psoriasis
 
	
 
Incidence and nature of AEs and SAEs
 
Application site tolerability assessment score
 
Change in clinical laboratory parameters, vital signs, and ECG from baseline
 

 
To evaluate the clinical effect of topically applied GSK2981278 relative to vehicle control in subjects with plaque psoriasis
 
	
 
Mean percent change in TPSS from baseline to Week 8
 
Mean percent change in PGA score from baseline to Week 8
 
Mean percent change in PASI from baseline to Week 8
 

Exploratory	

 
To explore exposure-response relationship of sparse systemic exposures with the clinical endpoints (by performing population PK/PD analysis, if required), as data allows
 
	
 
Plasma concentrations of GSK2981278 and clinical endpoints assessed to determine the clinical effect (e.g. TPSS, PGA, and PASI)
 

 
To evaluate the effect of GSK2981278 ointment on subject-reported outcomes
 
	
 
Mean percent change in Psoriasis Symptom Diary score from baseline to each study visit
 

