#### **5.1. Inclusion Criteria**

A subject will be eligible for inclusion in this study only if all of the following criteria apply:

AGE
1. 18 years of age and above, at the time of signing the informed consent.
TYPE OF SUBJECT AND DIAGNOSIS INCLUDING DISEASE SEVERITY
2. Subjects with clinical diagnosis of stable plaque psoriasis for $\geq 6$ months, as confirmed by the investigator. 3. Body surface area involvement $\geq 5\%$ and $\leq 15\%$ , excluding face and intertriginous areas, at Screening and Baseline ( Appendix 2 ). The area of psoriasis involvement may include up to 2% of total BSA on the scalp with only sparse terminal hair and/or vellus hair.

4. A PGA score of <math>\geq 2</math> at Baseline (Appendix 3)
 
5. One target plaque located on the trunk or proximal parts of extremities (excluding scalp, knees, and elbows) that is at least <math>9 \text{ cm}^2</math> in size at Screening and Baseline with a Target Plaque Severity Score (TPSS) <math>\geq 5</math> and induration subscore <math>\geq 2</math>. (Appendix 4)

--

SEX
-----

6. Male

Male subjects with female partners of child bearing potential must comply with the following contraception requirements from the time of first dose of study medication until 2 weeks after the last dose of study medication.

- Vasectomy with documentation of azoospermia. The documentation on male sterility can come from the site personnel's: review of subject's medical records, medical examination and/or semen analysis, or medical history interview.

- Male condom

The allowed method of contraception is only effective when used consistently, correctly and in accordance with the product label. The investigator is responsible for ensuring that subjects understand how to properly use these methods of contraception.

7. Female of non-reproductive potential (FNRP)

A FNRP is eligible to participate in this study if she meets at least one of the following conditions:

- Females with one of the following procedures documented and no plans to utilize assisted reproductive techniques (e.g., in vitro fertilization or donor embryo transfer):

- Bilateral tubal ligation or salpingectomy
- Hysteroscopic tubal occlusion procedure with follow-up confirmation of bilateral tubal occlusion
- Hysterectomy
- Bilateral Oophorectomy (surgical menopause)

- Post-menopausal women (including all women over 60 years of age, see below),

Post-Menopause criteria

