#### **7.4.2. Physician Global Assessment (PGA)**

The PGA is a clinical tool for assessing the current state/severity of a subject's psoriasis ([Appendix 3](#)). It is a static 5-point morphological assessment of overall disease severity, as determined by the investigator, using the clinical characteristics of erythema, plaque thickness, and scaling as guidelines. At each specified time point, the PGA is made without reference to previous scores. Variations of the PGA are frequently used in clinical studies because it is a simple assessment that is more similar to the assessments actually used in clinical practice [[Feldman, 2005](#)]. PGA will be assessed on the entire treated area (i.e. including the scalp lesion, if applicable).

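### PGA, a five-grade score, has mean percent change as its endpoint, so a one-grade improvement counts as 50%, 33% or 25% by entry grade

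*Protocol*

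**What the plan says.** Section 7.4.2 describes the PGA: "It is a static 5-point morphological assessment of overall disease severity". Section 5.1 requires a baseline PGA of at least 2.

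Section 3 lists "Mean percent change in PGA score from baseline to Week 8" as an endpoint under a Part B primary objective and as a Part A secondary endpoint; the synopsis (Section 1) does the same. For analysis, Section 9.4.1 (Part B) specifies "Mean percentage change in TPSS, PGA and PASI scores from baseline to each study visit", and Section 9.4.2 repeats this for Part A. Any comparison with vehicle is on the same scale: "statistical comparisons may be made as necessary between GSK arm and the Vehicle arm for mean percentage change from baseline to Week 8".

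The only grade-based PGA summary is the "proportion of subjects who achieve a PGA score of 0 or 1 and a minimum 2-grade improvement", which both sections list as an optional measure. Absolute change is listed for PASI but not for PGA.

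For the Part A PGA row, Section 9.2.1 assumes "50% reduction with 30% standard deviation will be observed" with N=8 and gives a 95% interval of 24.9% to 75.1%.

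**The concern.** Dividing the change in grade by the entry grade gives one step on the scale a different value for each entry grade, and only three entry grades are possible. The mean then combines how far subjects improved with where they started. Part A has 8 subjects and Part B is planned on 10 and 5 evaluable subjects, so the entry mix is largely a matter of chance. In a descriptive study the reported summary is the result. A reader who takes the PGA mean as an amount of improvement in grades could be misled, and in Part B could misjudge which arm improved by more grades.

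**Working it through.** **Inputs.** There are five grades (7.4.2) and entry is at 2 or above (5.1). The 0 to 4 range is inferred from five points together with the use of grades 0 and 1 in 9.4.1; the content of Appendix 3 is not in the public text. Evaluable sample: 8 in Part A, 10:5 in Part B (9.2.1). The entry-grade mixes below are assumptions, because the protocol gives none.

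**The plan's own figure.** Mean ± t(0.975, 7) × SD/√8 = 50 ± 2.365 × 30/√8 = 50 ± 25.1, which is 24.9 to 75.1. The stated interval is correct.

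**One step in percent.** Percent improvement = 100 × grades improved / entry grade.

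| Entry grade | 1 grade | 2 grades |
|---|---|---|
| 2 | 50.0% | 100% |
| 3 | 33.3% | 66.7% |
| 4 | 25.0% | 50.0% |

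**Mean when every subject improves by exactly one grade.**
- Half at 2, half at 3: 0.5 × 50 + 0.5 × 33.3 = 41.7%.
- 25/50/25 at 2/3/4: 0.25 × 50 + 0.5 × 33.3 + 0.25 × 25 = 35.4%.
- Half at 3, half at 4: 0.5 × 33.3 + 0.5 × 25 = 29.2%.

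**Reversed ranking at 10:5 (constructed example).**
- Ten subjects, six at grade 2 and four at grade 3, each improve one grade. Mean 1.0 grade; percent (6 × 50 + 4 × 33.3)/10 = 43.3%.
- Five subjects: three at grade 4 improve 2, 2 and 1 grades, and two at grade 3 improve 1 each. Mean 7/5 = 1.4 grades; percent (50 + 50 + 25 + 33.3 + 33.3)/5 = 38.3%.

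The arm with more grades improved has the lower percent change.

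**Chance difference between arms.** Every subject in both arms improves one grade, with entry grades drawn at random from the mix (simulated, 200,000 trials per mix).

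| Mix at 2/3/4 | SD of difference (points) | Beyond 5 points | Beyond 10 points |
|---|---|---|---|
| 30/60/10 | 4.7 | 28% | 3% |
| 25/50/25 | 5.0 | 32% | 4% |
| Equal thirds | 5.7 | 38% | 8% |

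For comparison, if the Part A PGA SD of 30 also held in Part B, the standard error of the between-arm difference would be 30 × √(1/10 + 1/5) = 16.4 points. The entry-mix component is roughly a third of that.

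**Section 9.2.1 in grades.** If all subjects entered at one grade, the planned 50% with half-width 25.1% would be 1.0 ± 0.50 grades (entry 2), 1.5 ± 0.75 (entry 3) or 2.0 ± 1.00 (entry 4).

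**The case against.** **Equal spacing.** Percent change is a legitimate relative measure, and calling two one-grade steps equal presumes equal spacing. This stands in part. A mean change in grades makes the same presumption, and the wording of the PGA grades is not available to judge it. The main display should therefore be the table of grades.

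**TPSS has the same feature.** One TPSS point is 20% from an entry score of 5 and 8.3% from 12, a wider ratio (2.4-fold) than for PGA (twofold). That is true. A single TPSS step, however, moves the result by at most 20 points on a 13-level scale, whereas a single PGA step moves it by 25 to 50 points. The coarseness makes PGA the case worth changing.

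**Low consequence.** Section 7.4.1 makes TPSS the primary measure of clinical effect, Section 4.1 bases the decision to proceed on TPSS, exposure and safety, and the Part B power table omits PGA. All of this stands and limits the weight of the point.

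**Leave it to the analysis plan.** Further summaries can be added there, but the protocol itself names percent change as the endpoint and as the scale for comparison with vehicle. The optional responder summary does not replace it.

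**Stronger readings that the documents do not support.**
- *The PGA result says nothing about effect size.* It still shows direction and relative change.
- *Part B is biased.* Arms are randomised. With balanced entry grades and the same one-grade response in both arms, the difference is zero.
- *The mean varies twofold.* The range 25% to 50% needs one cohort wholly at grade 4 and another wholly at grade 2.
- *The responder rule leans the opposite way.* In grades it requires 2, 2 and 3 from entry 2, 3 and 4, so it is hardest from grade 4, where percent change also gives least credit per grade.
- *Parts A and B cannot be compared.* No such comparison is planned.

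**Conclusion.** The point holds as a modest defect in how an endpoint is defined. For the same one-grade improvement, the PGA mean runs from about 29% to 42% across plausible mixed cohorts, and arms of 10 and 5 can be ranked against the order of grades improved. With identical responses in both arms, chance entry imbalance contributes a between-arm SD of about 5 points. That is noticeable, but smaller than the sampling error of about 16 points.

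This rests on the inferred 0 to 4 range, the assumed entry mixes and, for the 16-point figure, carrying the Part A SD into Part B. The 9.2.1 interval is correctly computed; what it lacks is a translation into grades. Neither the TPSS results nor the decision to proceed to Part B is affected.

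**What to change.** In Sections 1, 3, 9.4.1 and 9.4.2, define the PGA endpoint as change in grade from baseline to Week 8. Present it as counts of Week 8 grade by baseline grade and of number of grades improved, with mean or median change as a summary. Keep percent change in PGA as supportive only, and put any comparison with vehicle on the grade scale. TPSS and PASI stay as they are.

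In Section 9.2.1, keep the PGA row and add the precision in grades: with N=8 the 95% half-width is 2.365/√8 = 0.84 times the assumed SD in grades.

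The cost is wording and one small table, with no new data, visits or subjects. PGA would no longer share a percent axis with TPSS and PASI. A mean change in grades still assumes equal spacing, which is why the table of grades should be the main display.

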Objectives	Endpoints
Primary	

 
To evaluate the safety and tolerability of topically applied GSK2981278 and its vehicle in subjects with plaque psoriasis
 
	
 
Incidence and nature of AEs and SAEs
 
Application site tolerability assessment score
 
Change in clinical laboratory parameters, vital signs, and ECG from baseline
 

 
To evaluate the clinical effect of topically applied GSK2981278 relative to vehicle control in subjects with plaque psoriasis
 
	
 
Mean percent change in TPSS from baseline to Week 8
 
Mean percent change in PGA score from baseline to Week 8
 
Mean percent change in PASI from baseline to Week 8
 

Exploratory	

 
To explore exposure-response relationship of sparse systemic exposures with the clinical endpoints (by performing population Pharmacokinetic (PK)/Pharmacodynamic (PD) analysis, if required), as data allows
 
	
 
Plasma concentrations of GSK2981278 and clinical endpoints assessed to determine the clinical effect (e.g. TPSS, PGA, and PASI)
 

 
To evaluate the effect of GSK2981278 ointment on subject-reported outcomes
 
	
 
Mean percent change in Psoriasis Symptom Diary score from baseline to each study visit
 

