## 4. STUDY DESIGN

### 4.1. Overall Design

This is a single-center, 2-part Phase I/IIa study to evaluate the safety, tolerability, clinical effect and systemic exposure potential of topically applied GSK2981278 ointment in subjects with plaque psoriasis. Drug delivery into the skin and changes in the relevant biomarkers will be explored using skin punch biopsies as well.

- Part A: open label, single arm study
- Part B: double-blind, randomized, 2-arm, parallel-group, vehicle-controlled study

After completion of Week 4 assessments and Week 8 assessments in Part A, the Sponsor will review the safety, tolerability, PK and clinical effect data. If data demonstrates a mean percent reduction of 40% or greater in TPSS from baseline and systemic exposure levels below the NOAEL determined in the pre-clinical toxicity studies without significant safety or tolerability issues at either time point, the study will proceed to Part B.

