#### **4.4. Design Justification**

Single-arm, open-label Part A will allow focused evaluation of safety, tolerability, clinical effect, and systemic exposure potential and the exploration of drug delivery to the skin and changes in relevant gene expressions following topically applied GSK2981278 ointment in a small number of subjects without exposing additional subjects to unnecessary burdensome assessments.

Treatment duration of 8 weeks is considered sufficiently long to look for the signal of drug effect and determine whether GSK2981278 may be a viable candidate for development as a topical treatment for plaque psoriasis.

The number of subjects proposed in this study is expected to provide reasonable information on the clinical effect, gene expression changes, and drug delivery into the psoriatic skin.

[figure not shown]
If data from Part A demonstrate sufficient signal of drug effect to meet the pre-defined criteria to proceed to Part B, any clinical effect observed in Part A will be further evaluated in a randomized, double-blind, vehicle-controlled fashion in Part B. Inclusion of the vehicle group will inform the treatment effect relative to the vehicle effect.

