#### **7.4.1. Target Plaque Severity Score (TPSS)**

A target lesion of at least 9 cm^2 with a TPSS  $\geq 5$  and an induration subscore  $\geq 2$  will be selected at baseline. The severity of erythema, scaling, and induration (plaque thickness) will be assessed by the investigator on a 5-point scale ranging from 0=none to 4=very marked ([Appendix 4](#)). A total score will be calculated by adding the individual scores (13-point scale; maximum score 12). TPSS is the primary measure of clinical effect for this study.

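### Does leaving the Part B active-versus-vehicle comparison optional in Section 9.4.1 undercut the primary objective of effect relative to vehicle?

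*Protocol*

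**What the plan says.** The protocol's objectives tables (Synopsis and Section 3) list a Part B primary objective: "To evaluate the clinical effect of topically applied GSK2981278 relative to vehicle control in subjects with plaque psoriasis". Its endpoints are the mean percent changes in TPSS, PGA and PASI from baseline to Week 8. Section 4.4 gives the reason for the control arm: "Inclusion of the vehicle group will inform the treatment effect relative to the vehicle effect". Section 7.4.1 states that "TPSS is the primary measure of clinical effect for this study". TPSS is also the only efficacy measure in the rule for moving from Part A to Part B, which requires "a mean percent reduction of 40% or greater in TPSS from baseline" (Section 4.1).

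On analysis, Section 9.1 states: "No formal hypothesis tests are planned". It assigns the key objectives, clinical effect included, to descriptive statistics. For Part B, Section 9.4.1 requires summaries of percent change on all three measures: "scores from baseline to each study visit will be summarized based on the per protocol analysis set". It then adds that "statistical comparisons may be made as necessary between GSK arm and the Vehicle arm for mean percentage change from baseline to Week 8", for the same three scores.

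Section 9.2.1 explains the numbers: "Sample size is based on feasibility and the estimated number of subjects expected to provide reasonable information on the key objectives of the study". At 10 active and 5 vehicle subjects in Part B, it gives power of 71.7% for TPSS and 92.1% for PASI, based on a two-sample t test at 5%. For Part A it gives expected 95% confidence intervals instead.

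**The concern.** The objective is comparative, but the only comparative analysis in the protocol is permissive. Nothing says when a comparison becomes necessary, and no between-arm difference or interval is promised. The permissive sentence also covers three scores without order, although TPSS is ranked first elsewhere.

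Two harms seem possible. Part B might be reported without the contrast that it was randomized to provide. Or the sponsor might look at three contrasts and present the one that reads best. If three unadjusted 5% tests were run and any one was taken as evidence, the chance of at least one false positive would exceed 5%.

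Section 9.2.1 adds to the unease, because it describes Part B by its power to reject a null hypothesis that Section 9.1 does not plan to test. With about five vehicle subjects, the precision of the difference also decides how it can be read, so one would want to be sure of seeing it.

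**Working it through.** **1. The protocol's own figures (Section 9.2.1, Part B).** Inputs: 10 active, 5 vehicle, SD 20, alpha 5%; assumed reductions of 50% against 20% for TPSS (difference 30) and 50% against 10% for PASI (difference 40).

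- Standard error of the difference: 20 × √(1/10 + 1/5) = 20 × 0.5477 = 10.95.
- Noncentrality: 30 / 10.95 = 2.74 for TPSS; 40 / 10.95 = 3.65 for PASI.
- Power from the noncentral t with 13 degrees of freedom, two-sided 5%: 71.65% for TPSS and 92.09% for PASI.

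These match the stated 71.7% and 92.1%. One-sided t tests give 82.8% and 96.5%, and the two-sided normal approximation gives 78.2% and 95.5%. So the table rests on the two-sided t test and is correct.

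**2. What the required summaries already deliver.** Half-width of the 95% interval for active minus vehicle = t(df, 0.975) × SD × √(1/n1 + 1/n2).

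| Evaluable | df | Half-width | TPSS, difference 30 | PASI, difference 40 |
|---|---|---|---|---|
| 10:5 | 13 | 2.160 × 10.95 = 23.7 | 6.3 to 53.7 | 16.3 to 63.7 |
| 12:6 (all 18) | 16 | 2.120 × 20 × 0.5 = 21.2 | 8.8 to 51.2 | 18.8 to 61.2 |

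Every input is an n, a mean or an SD by arm, which a usual descriptive table shows. The half-widths depend on the number of subjects and the SD, not on the wording of Section 9.4.1. The protocol gives no Part B SD for PGA, so no PGA interval is computed.

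**3. How much freedom is really left.**

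| Element | Status in the protocol |
|---|---|
| Summaries of TPSS, PGA and PASI | Required at every visit (9.4.1) |
| Variable and time point for any comparison | Fixed: mean percentage change at Week 8 (9.4.1) |
| Analysis set for the summaries | Fixed: per protocol (9.3.1, 9.4.1) |
| Leading endpoint | Fixed: TPSS (7.4.1) |
| Formal test or success rule for Part B | None (9.1) |
| Printing the difference and its interval | Open |

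**4. Size of the multiplicity worry.** With three independent 5% tests the chance of at least one false positive is 1 − 0.95³ = 14.3%. By simulation at 10:5 it is about 12.5% at a correlation of 0.5 and about 10% at 0.8; both correlations are assumptions. These rates apply only if all three contrasts are tested without adjustment and any one is read as proof. The protocol attaches no such reading to Part B.

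**The case for a change.** The strongest case for a change is that this is a rule the protocol states, not a silence. A SAP that kept the comparison optional would comply. Optional testing is defensible in a small Phase I/IIa study, but optional reporting of a contrast named in a primary objective is harder to defend. A difference with a 95% interval is estimation, so it fits a plan without tests, and Part A is already described by expected intervals. The interval at 10:5 is wide, and readers should not have to calculate it. The change would be wording only, at no cost in data or patients.

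Part of this stands. No section promises the interval, and Section 9.4.1 does not say in words that its Part B summaries are shown by arm. A line in the SAP giving the Week 8 TPSS difference with a two-sided 95% interval, with PASI and PGA as support, would be good practice.

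It does not show a defect in the protocol. The endpoints listed for the objective are mean percent changes, and these are required. A favourable result on one score could not hide the other two. Section 9 refers the reader to the SAP for analysis detail, and the choice of which comparisons to show, and in what form, is ordinary SAP content. Replacing correct power figures with half-widths in Section 9.2.1 would be a matter of preference, since the sample size rests on feasibility.

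**Conclusion.** No change is needed. The permissive wording agrees with a plan that is descriptive throughout, and following it gives no wrong number and no wrong decision. The information that the objective asks for is in the required summaries: the difference by subtraction, and its interval from n and SD, with a half-width of 23.7 points at 10:5 or 21.2 at 12:6 for an SD of 20. TPSS already leads, and the only efficacy decision rule in the protocol belongs to Part A. The power figures in Section 9.2.1 reproduce, and the design does not depend on them.

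This rests on two assumptions. The first is that the Part B summaries are presented by treatment arm with n, mean and SD, which is the natural reading for a randomized, vehicle-controlled part. The second is that no confirmatory claim is drawn from a single comparison chosen among the three. What remains is a gap in presentation that an analyst would fill sensibly in the SAP.
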